6.1.4. Medical Devices

The combination products used in the study are tirzepatide investigational SDP and a marketed insulin glargine prefilled injection pen.

6.2. Preparation, Handling, Storage, and Accountability

1. The investigator or designee must confirm appropriate storage conditions have been maintained during transit for all study drug(s) received and any discrepancies are reported and resolved before use of the study drug(s).

2. Only participants enrolled in the study may receive study drug(s). Only authorized study personnel may supply, prepare, or administer study drug(s). All study drug(s) must be stored in a secure, environmentally controlled, and monitored (manual or automated) area in accordance with the labeled storage conditions with access limited to the investigator and authorized study personnel.
3. The investigator or authorized study personnel are responsible for study drug(s) accountability, reconciliation, and record maintenance (that is, receipt, reconciliation, and final disposition records).
4. Further guidance and information for the final disposition of unused study drug(s) are provided in the Study Reference Manual.

6.3. Measures to Minimize Bias: Randomization and Blinding

This study is designed as a randomized, double-blind study to minimize bias.

Participants who meet all criteria for enrollment will be randomized to one of the study treatment groups at Visit 3. Assignment to treatment groups will be determined by a computer-generated random sequence using an interactive web-response system (IWRS). Participants will be randomized in a 1:1:1:1 ratio to receive tirzepatide 5 mg, 10 mg, 15 mg, or matched placebo.

The randomization will be stratified based on HbA1c ($\leq 8.0\%$ or $> 8.0\%$ [≤ 64 , > 64 mmol/mol]), and SGLT-2i use (Yes or No).

To preserve the blinding of the study, a minimum number of Lilly personnel will see the randomization table and treatment assignments before the study is complete.

Emergency codes, generated by a computer drug labeling system, will be available to the investigator. These codes, which reveal the participant's treatment group when opened, may be opened during the study ONLY if the participant's well-being requires knowledge of the participant's treatment assignment.

Emergency unblinding for AEs may be performed through the IWRS, which may supplement or take the place of emergency codes generated by a computer drug-labeling system. This option may be used ONLY if the participant's well-being requires knowledge of the participant's treatment assignment. All calls resulting in an unblinding event are recorded and reported by the IWRS.

If an investigator, site personnel performing assessments, or participant is unblinded, the participant must be discontinued from the study. In cases where there are ethical reasons to have the participant remain in the study, the investigator must obtain specific approval from a Lilly clinical research physician (CRP) for the participant to continue in the study.

In case of an emergency, the investigator has the sole responsibility for determining if unblinding of a participant's treatment assignment is warranted for medical management of the event. The participant safety must always be the first consideration in making such a determination. If a participant's treatment assignment is unblinded, Lilly must be notified immediately. If the investigator decides that unblinding is warranted, it is the responsibility of the investigator to promptly document the decision and rationale and notify Lilly as soon as possible.

6.4. Study Intervention Compliance

Study drug compliance will be determined by the following:

- Study drug administration data will be recorded by the participant and reviewed by the investigator at each study visit.
- The participants will be instructed to return any unused study drug and/or empty cartons at the next visit to the study site for the purpose of performing drug accountability.

In the 3 tirzepatide treatment groups, as well as the placebo group, treatment compliance is defined as taking at least 75% of the required doses of study drug. Similarly, a participant will be considered noncompliant if he or she is judged by the investigator to have intentionally or repeatedly taken more than the prescribed amount of medication.

In addition to the assessment of a participant's compliance with the study drug administration, other aspects of compliance with the study treatments will be assessed at each visit based on the participant's adherence to the visit schedule, completion of study diaries, the results of home BG monitoring, and any other parameters the investigator considers necessary.

Participants considered not to be compliant with their medication and/or the study procedures will receive additional training and instruction, as required, and will be reminded of the importance of complying with the protocol.

6.5. Dose Modification

6.5.1. Tirzepatide

Please refer to Section 6.1.1 for tirzepatide administration. Study drug dose modification is not permitted except for management of intolerable GI symptoms (see Section 6.5.1.1).

6.5.1.1. Management of Participants with Gastrointestinal Symptoms

In participants who experience intolerable Gastrointestinal symptoms (for example, nausea, vomiting, or diarrhea) at any time during the study, the following measures are recommended:

1. counseling on dietary behaviors that may help mitigate nausea and vomiting, (for example, eating smaller meals, splitting 3 daily meals into 4 or more smaller ones, and stopping eating when they feel full).
2. if symptoms persist despite #1, prescribing symptomatic medication (for example, antiemetic or antidiarrheal medication), at the investigator's discretion
3. if symptoms persist despite #1 and #2, interrupting study drug for 1 dose, provided the participant has taken the last 3 weekly doses. Study treatment should be resumed at the assigned dose immediately, either alone or in combination with symptomatic medication, which can also be utilized to manage symptoms (Section 6.8). Management of study drug after interruptions >1 dose is discussed in Section 7.1.2.

If intolerable GI symptoms (for example, nausea, vomiting, or diarrhea) persist despite the above measures after Visit 11 (after the scheduled visit in Week 8) the investigator should contact Lilly to consider continuing treatment at a lower maintenance dose of study drug in a blinded fashion, for example:

- Participants at 5 mg will decrease the dose to placebo.
- Participants at 7.5 mg or 10 mg will decrease the dose to 5 mg.
- Participants at 12.5 mg or 15 mg will decrease the dose to 10mg.

If de-escalation of the tirzepatide dose is necessary, the investigator will use the interactive web-response system (IWRS) to receive the appropriate tirzepatide dispensing information. If de-escalation is needed between scheduled visits, the IWRS will have unscheduled visits (for example, Visit 13a) dedicated to provide dispensing information for participants whose dose has been de-escalated. Those participants who have their dose de-escalated, will not be escalated again. The dose can be de-escalated only once. After that, the participants will have to discontinue study drug if intolerable GI AE persists and stay in the study.

If intolerable persistent GI symptoms occur, the investigator should take the above measures to keep the participant on study treatment. However, after the escalation period (Week 24), dose decreases will not be allowed.

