- Treatment condition:* The randomized treatment. Further details on study treatment and rescue therapy can be found in Section 6.

- *Intercurrent event:* Intercurrent events of interest: “Treatment discontinuation for any reason” and “Initiation of antihyperglycemic rescue treatment” will be addressed using the following strategies:
 - Had participants stayed on treatment (hypothetical strategy).
 - Had participants not taken antihyperglycemic rescue medication (hypothetical strategy).
- *Population-level summary:* Difference in mean changes between treatment conditions.

Secondary estimand

A robustness of the primary efficacy assessment, guided by the “treatment-regimen” estimand, will be conducted. This estimand aims at reflecting how participants with T2DM are treated in clinical practice and takes into account both tolerability and efficacy.

The treatment-regimen estimand answers the following question of interest for the primary objective: What is the treatment difference in change from baseline in HbA1c after 40 weeks of treatment in participants with T2DM regardless of treatment discontinuation for any reason and regardless of initiation of antihyperglycemic rescue?

The treatment-regimen estimand is described by the following attributes.

- *Population:* Participants with T2DM inadequately controlled on insulin glargine alone or in combination with metformin with or without SGLT-2i.
- *Endpoint:* Change from baseline to week 40 after randomization in HbA1c.
- *Treatment condition:* The randomized treatment regardless of adherence to treatment with or without antihyperglycemic rescue medication. Further details on study treatment and rescue therapy can be found in Section 6.
- *Intercurrent events:* Intercurrent events of interest: “treatment discontinuation for any reason” and “initiation of rescue antihyperglycemic treatment” are addressed by the treatment condition.
- *Population-level summary:* Difference in mean changes between treatment conditions.

Both the efficacy and treatment-regimen estimands will be evaluated for the primary and all key secondary objectives. The population, treatment condition, intercurrent events, and population-level summary specified above for each estimand for the primary objective will also apply to the key secondary objectives. The endpoint for each key secondary objective is defined in the table above.

4. Study Design

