5.4. Screen Failures

A screen failure occurs when a participant who consents to participate in the clinical study is not subsequently randomly assigned to study drug. A minimal set of screen failure information is required to ensure transparent reporting of screen failure participants to meet the Consolidated Standards of Reporting Trials (CONSORT) publishing requirements and to respond to queries from regulatory authorities. Minimal information includes demography, screen failure details, eligibility criteria, and any serious adverse event (SAE).

Individuals who do not meet the criteria for participation in this study (screen failure) must not be rescreened.

5.5. Criteria for Temporarily Delaying Enrollment/Randomization/Administration of Study Intervention of a Participant

Not applicable.

6. Study Intervention(s) and Concomitant Therapy

Study intervention is defined as the study drug (tirzepatide 3 doses or placebo) intended to be administered to a study participant according to the study protocol.

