6.1. Study Intervention(s) Administered

Assignment to tirzepatide (3 doses) or placebo will occur at randomization. Beginning at randomization, all participants will receive study drug according to the randomized treatment group for the duration of the 40-week treatment period. Following randomization, the participant will inject the first dose of study drug/placebo at the study site. The date and time of all doses of study drug should be recorded on the eCRF.

This table lists the interventions used in this clinical study.

Group Name	Tirzepatide 5 mg	Tirzepatide 10 mg	Tirzepatide 15 mg	Placebo	Concomitant background insulin for all treatment arms
Intervention Name	Tirzepatide 5 mg	Tirzepatide 10 mg	Tirzepatide 15 mg	Placebo	Insulin Glargine U100
Dosage Level(s)	5 mg QW	10 mg QW	15 mg QW	NA	Titrated
Route of Administration	SC				
Frequency of Administration	QW				QD
Use	Experimental intervention			comparator	Concomitant background insulin
Sourcing	Provided centrally by the Sponsor and dispensed via IWRS				
Packaging and Labeling	Will be provided in autoinjectors (single-dose pens) and packaged in cartons to be dispensed. Clinical study materials will be labeled according to country regulatory requirements.				

Abbreviations: IWRS= interactive web-response system, QD= once daily, QW=once weekly, SC=subcutaneous.

[figure not shown]

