6.8. Concomitant Therapy

Participants will be permitted to use concomitant medications that they require during the study, except certain medications that may interfere with the assessment of efficacy and safety characteristics of the study treatments ([Table GPIM.2](#)).

Antihyperglycemic medications other than study drugs are ONLY allowed during these circumstances:

- for participants who require permanent discontinuation of tirzepatide but remain in the study.
- for rescue therapy after randomization due to severe, persistent hyperglycemia
- during the safety follow-up period.

GLP-1 RAs, DPP 4 inhibitors, pramlintide, and other basal insulins are prohibited medications and are not allowed during the study. Short-term treatment with a nonstudy insulin for up to 14 days is allowed for certain clinical situations, for example, elective surgery, during hospitalization, or hyperosmolar states (this will not be considered as rescue therapy).

Investigative site personnel will inform participants that they must consult with the investigator or a designated site personnel member upon being prescribed any new medications during the study. This may not be possible when initiated for treatment of medical emergencies, in which case, the participant will inform the investigator or a designated site personnel member as soon as possible. Any additional medication initiated during the course of the study (including over the counter [OTC] drugs, such as paracetamol or aspirin) must be documented, and the name of the drug and the date(s) of administration must be recorded on the “Concomitant Medications” section of the eCRF.

All nonstudy medications will be recorded on source documents at all visits.

Nonstudy medications taken by participants who are screened, but not randomized will not be reported to Lilly unless an SAE or AE occurs that the investigator believes may have been caused by a study procedure.

Table GPIM.2. Use of Concomitant Medications that May Interfere with Efficacy and Safety Assessments

Drug Class	Use During Screening/Lead-In	Conditions for Use after Randomization		
		Acute therapy ^a	Rescue therapy	During Safety Follow-Up Period
Drugs with approved weight loss indication ^b	Excluded	N	N/A	N
Systemic glucocorticoid therapy ^c	Excluded except for acute therapy ^a	Y	N/A	N (except for acute therapy ^a)
Antihyperglycemia medications				
GLP-1 RAs and related fixed-dose combination	Excluded	N	N	N

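### Must the blinded step from 5 mg to placebo be declared a discontinuation of treatment for the efficacy estimand?

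*Protocol*

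**What the plan says.** **The step.** After Visit 11 (Week 8), if dietary advice, symptomatic medication and a skipped dose have not helped, Protocol 6.5.1.1 has the investigator contact the sponsor to "consider continuing treatment at a lower maintenance dose of study drug in a blinded fashion". One of the listed steps is "Participants at 5 mg will decrease the dose to placebo"; the others go from 7.5 or 10 mg to 5 mg and from 12.5 or 15 mg to 10 mg. The step is final: "Those participants who have their dose de-escalated, will not be escalated again". It is allowed once, and not after Week 24. Stopping is a separate, later event: "After that, the participants will have to discontinue study drug if intolerable GI AE persists and stay in the study".

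**The estimand.** Protocol Section 3 and SAP 1.1 name two intercurrent events for the efficacy estimand, treatment discontinuation (permanent discontinuation in the SAP) and rescue, both handled by a hypothetical strategy. The protocol gives the treatment condition as "The randomized treatment. Further details on study treatment and rescue therapy can be found in Section 6". SAP 1.1 keeps the first sentence and omits the pointer to Section 6.

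**The data sets.** The EAS removes data after rescue and after stopping study drug (Protocol 9.2) or after permanent discontinuation of treatment (SAP Table GPIM.3.1). SAP 4.1 analyses by randomized maintenance dose, whatever was actually received. SAP 4.3.4 defines a retrieved dropout as someone who stopped study drug early but has a Week 40 value. It changes the imputation method if any group has four or fewer.

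**The concern.** The estimand asks what would have happened had participants stayed on their randomized treatment. A 5 mg participant moved to placebo has stopped tirzepatide for good, and by Week 40 has been off it for between 40 − 24 = 16 and 40 − 8 = 32 weeks. If those HbA1c, weight and fasting glucose values enter the repeated-measures model as on-treatment 5 mg data, the model estimates something other than the stated hypothetical.

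Three things would be at stake:

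- The 5 mg estimate would be pulled toward placebo.
- The 5 mg tests of HbA1c and weight (H5,1 and H5,2) gate everything from H15,3 onward in SAP 2.1, so power lost at 5 mg carries over to later tests at the higher doses.
- The status of one or two switchers could move a group across the four-patient threshold in SAP 4.3.4 and so select the imputation method for the treatment-regimen estimand.

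**Working it through.** **1. Does the text leave two data sets open?** Five provisions bear on the operational status of a switcher:

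- Protocol 6.5.1.1 describes the step as continuing treatment, states its aim as keeping the participant on study treatment, and places discontinuation after it.
- Protocol Section 6 includes placebo in study drug: "Study intervention is defined as the study drug (tirzepatide 3 doses or placebo) intended to be administered to a study participant".
- Both EAS definitions cut at stopping or permanent discontinuation, not at a change of dose.
- SAP 4.1 keeps the participant in the randomized arm.
- SAP 6.2 counts study drug injections for compliance regardless of the dose they contained.

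All five point the same way: the switcher is still on study drug and later data stay in the EAS. By the same wording the switcher has not discontinued study drug, so is not a retrieved dropout under SAP 4.3.4; an observed Week 40 value enters the full analysis set as it stands. If the participant later stops injecting, the EAS cut-off and the retrieved-dropout definition apply from then on.

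**2. Which arms?** On the planned escalation, the 10 and 15 mg arms are at 7.5 mg or more after Week 8, so the step to placebo falls on the 5 mg arm. An exception would need an interruption that leaves a higher-dose participant at 5 mg (Protocol 7.1.2). The primary tests are essentially untouched.

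**3. How large is the dilution?** Inputs from Protocol 9.5: difference 0.95, SD 1.3, two-sided alpha 0.025, 25% loss, 64 per arm.

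The plan's own figure first. Evaluable per arm: 64 × 0.75 = 48. Noncentrality: 0.95 / (1.3 × √(2/48)) = 3.58 on 94 degrees of freedom. Power is 90.2% at 0.025 and 94.3% at 0.05. In reverse, 48 / 0.75 = 64 and 4 × 64 = 256, as stated.

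Now suppose k switchers in the 5 mg arm. Assumptions that are not in the documents: the 5 mg effect is also 0.95; it is wholly lost by Week 40; and the switchers come from within the planned 25%, so keeping them gives 48 + k against 48 and excluding them gives 48 against 48. With f = k/(48 + k):

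- expected difference = 0.95 × (1 − f)
- SD in the 5 mg arm = √(1.3² + f(1 − f) × 0.95²)

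| k | Difference | Power at 0.05 | Power at 0.025 |
|---|---|---|---|
| excluded | 0.950 | 94.3% | 90.2% |
| 1 kept | 0.931 | 93.6% | 89.0% |
| 2 kept | 0.912 | 92.8% | 87.8% |
| 5 kept | 0.860 | 90.2% | 84.1% |

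From the rounded figures, the loss at 0.05 is 0.7, 1.5 and 4.1 points. If only half the effect is lost, five switchers give 0.905 and 93.2% at 0.05 (88.5% at 0.025). If five switchers come on top of the 25%, keeping them gives 88.0% against 93.1% excluded at 0.05, and 81.2% against 88.3% at 0.025.

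Five switchers (5/64 = 7.8% of the arm) is a stress case without a source. No figure can be given for body weight, because the documents state no weight effect or SD.

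**The case for a change.** The best case for a change is that no sentence classifies the step, and some wording points the other way. Protocol 6.1 says that "all participants will receive study drug according to the randomized treatment group for the duration of the 40-week treatment period", and Protocol 6.8 has a provision "for participants who require permanent discontinuation of tirzepatide but remain in the study", which speaks of tirzepatide rather than of study drug. A 5 mg participant on placebo has plainly left the randomized dose. Because the content of the step differs by arm only after unblinding, a rule not written beforehand could look post hoc. A few SAP sentences and one derived flag would settle it.

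Part of this stands. The estimand wording and the operational wording do not match neatly, more so in the SAP, which drops the pointer to Section 6. In the protocol that pointer arguably brings the step-down rule inside the treatment condition.

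The remedy is where the case weakens. Declaring the step a discontinuation would exclude data in tirzepatide arms but not after a sham step in the placebo arm. It would rest on missing-at-random for people selected for intolerance, and might raise the 5 mg estimate; a conservative default would give way to a potentially favourable one. Disposition and study-drug discontinuation summaries would still show these participants on study drug, so the event would not have a single status. A rule for the placebo step alone would also leave the steps to a lower active dose unclassified, and those reach the primary arms. Nor is the reading an after-the-fact choice: it follows from text already fixed.

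**Conclusion.** No change follows. What is missing is an explicit classification, and the existing text fills it: the stepped-down participant is on study drug, stays in the EAS under the randomized arm, and is not a retrieved dropout. The cost is an estimate for 5 mg that leans toward no difference, with no inflation of type I error and the primary comparisons essentially unaffected. For one or two switchers that is 0.7 to 1.5 power points on H5,1 at 0.05, under the unsourced assumptions of a 0.95 effect at 5 mg and its complete loss. It would be larger if switching were common, but the step is a last resort, needs contact with the sponsor, and closes at Week 24.

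Keeping the data is coherent once the treatment condition is read with its pointer to Section 6. Excluding them trades a conservative bias for a possible favourable one. A statistician could defend either, and the plan's choice needs no correction. If step-downs prove frequent, SAP 4.1 already permits additional analyses without amending the plan, so counts by arm and an analysis without the later data can be reported then. None of this takes a view on the dosing rule.

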6.5.2. Background Antihyperglycemic Medications

1. If increased risk of hypoglycemia during the period between 2 insulin dose assessments is judged to be related to the treatment regimen, the following changes should be made:
 - Decrease the insulin glargine dose by 2 U, per the TTT algorithm, in the following cases:
 - If ≥ 2 episodes of nonsevere hypoglycemia (<3.9 mmol/L [<70 mg/dL]) were recorded at any time during the day for the assessment period; and/or
 - If ≥ 1 episode that met the criteria for severe hypoglycemia (events requiring assistance to administer therapy) or was associated with SMBG value <3.0 mmol/L (<54 mg/dL) was recorded during the assessment period; and/or
 - If the median FPG value for the assessment period is <4.4 mmol/L (<79 mg/dL).
 - In the case of repeated hypoglycemic events, even with a very low glargine dose and despite glargine dose decreases per the TTT algorithm, administration of insulin glargine may be temporarily or permanently discontinued.
 - If increased risk of hypoglycemia persists despite discontinuation of insulin glargine, then dose reduction or discontinuation of OAMs (for participants who are taking) should be considered.
2. In certain situations, short-term discontinuation will be allowed in line with the product(s) labeling (for example, for metformin: severe dehydration, elective surgery, or need for radiologic examination involving intravenous injection of iodinated contrast dye; for SGLT-2i: ketoacidosis or clinical condition known to predispose to ketoacidosis [eg, prolonged fasting due to acute illness or surgery]). Once the situation that led to temporary discontinuation of the drug resolved, treatment should be restarted at investigator discretion.

3. If a participant develops contraindications to metformin or SGLT-2i (if used), such that the use of the drug is contraindicated according to the country specific label (eg, eGFR [CKD-EPI] lower than the threshold defined in country specific label), the drug should be discontinued; in this case, the insulin glargine dose may need to be further adjusted.

A participant will be considered noncompliant with the protocol (protocol deviation) if he or she changes the dose, or discontinues metformin or SGLT-2i (if used) for reasons other than those described here. Doses of background OAMs could be increased as rescue therapy for severe, persistent hyperglycemia, at the discretion of investigators (see Section [8.3.4.2](#) for details).

